1. OBJECTIVES

1.1 Study Design

This is a pilot study designed to characterize the effects of high energy radiation on human bone degradation, with a specific interest in reducing the rate of sacral fractures.

Figure 1: Phase Transition into Clinical Trials

Based on the data published in animal models, we hypothesized that bone degradation after irradiation is associated with clinically detectable changes in serum markers, bone density, and bone architecture. This study is a step towards better characterizing those changes in humans, and understanding the mechanism of the underlying pathology. The results of this research may ultimately lead to the development of interventions aimed at reducing the burden of radiation-induced fractures, as outlined in Figure 1:

Figure 2 provides a succinct layout of the proposed experimental plan and a summary of the data we expect to collect.

Figure 2: Experimental Design Summary

In vivo (patient labs + imaging)	In vitro (bone biopsies)	Experimental Design. We plan to conduct in vivo and in vitro studies to characterize radiation-induced changes in bone. We will look at changes in the cellular composition of bone, bone metabolism, microscopic architecture, and mechanical properties.

 ▪ Serum markers ▪ QCT 	
 ▪ Undecalcified histology ▪ Tetracycline double staining ▪ Micro-CT ▪ Electron scattering microscopy ▪ Nanoindentation 	

1.2 Primary Objectives

- 1.2.1 To measure the effect of high doses of radiation on trabecular bone mineral density (Tb. TBD) in the adult sacrum using the quantitative computer tomography technique (QCT) in patients undergoing treatment with combination surgery and adjuvant radiotherapy, or radiation alone.

CONFIDENTIAL

This document is confidential. Do not disclose or use except as authorized.

1.3 Secondary Objectives

- 1.3.1 To characterize changes in the levels of serum markers of bone turnover during the course of 12 months following treatment with high doses of radiation
- 1.3.2 To analyze the effects of high doses of radiation on the structure and mechanical properties of bone by microscopic computer tomography (micro-CT), and nanoindentation
- 1.3.3 To characterize the effect of high doses of radiation on the dynamic parameters of bone turnover (e.g. mineral apposition rate, mineral formation rate, and mineralization lag time) by tetracycline quadruple labeling method
- 1.3.4 To characterize the effect of high doses of radiation on the mineralized and cellular components of bone architecture (e.g. volume, thickness, separation of trabecular bone, and osteoid surface and volume) by undecalcified bone histology

2. BACKGROUND

2.1 Rationale

[figure not shown]
External beam radiation plays an important role in the management of bone malignancies. In combination with surgical resection, high dose radiation was shown to significantly improve survival in historically difficult to treat tumors [4, 6, 15, 22]. The detrimental effects of radiation increase proportionally with the dose delivered. Even at relatively low doses of radiation (30 to 40 Gy), skeletal complications such as radiation-induced osteoporosis, insufficiency fractures (see

Figure 3), physeal arrest, and non-union are common [2, 14, 21, 29, 33]. At high doses (70 Gy and above), the rate of bone-related complications increases dramatically. Despite the high rate of complications, high-dose radiation is becoming increasingly more utilized because of its positive effects on patient survival and prevention of recurrence. For example, combination of surgery and adjuvant radiation doses of greater than 70 Gy achieves meaningful control of locally aggressive tumors (like sacral chordomas), that otherwise have a very high rate of recurrence [6].

CONFIDENTIAL

This document is confidential. Do not disclose or use except as authorized.

Figure 3: Bilateral Sacral Fractures

Given its growing significance in the treatment of malignant bone tumors, we propose to investigate the impact of high dose radiation (over 70 Gy) on human bone metabolism, architecture, and mechanical properties. It is presently unknown what biological mechanisms and structural changes occur in human bone in response to high doses of radiation. Local effects on bone may differ for different parts of the body. To minimize the variability in bone properties, we have chosen to focus this study on one type of bone - the sacrum. Still, our results are likely to be generalizable to other bones because of the common physiology. Sacrum is a particularly good target for this study because 1) tumors affecting the sacrum are often treated with high doses of radiation and 2) sacrum is one of the bones maximally affected by post-radiation complications.

Figure 3 shows a schematic representation of a typical insufficiency fracture that can occur in the sacrum after radiation treatment. Our group recently reported the rate of sacral insufficiency fractures as high as 64% in patients treated with high dose radiation and surgery (submitted). Thus, for the purposes of this pilot study we will focus on patients with primary malignant tumors of the sacrum.

Most MGH patients with sacral tumors are treated with combination of surgery and adjuvant radiation. They receive 50.4 Gy of photon/proton beam radiation before surgery, in accordance with the protocol summarized in Figure 9 (A). After the tumor is surgically removed, patients receive another 19.8 Gy of radiation, for a total dose of 70.2 Gy. We plan to enroll 20 patients treated in this fashion into the “Surgical Arm” of the study. It has been previously suggested that in patients treated with combination of surgery and radiation, the high rate of sacral fractures may be partially attributable to surgery. Yet, sacral fractures have been reported in patients who were treated with radiation alone. There is no data to date that can account for these observations. To explore this question, we plan to enroll 10 patients treated with radiation alone into the “Non-surgical Arm” of our study. These patients receive between 72 Gy

CONFIDENTIAL

This document is confidential. Do not disclose or use except as authorized.

(osteosarcoma and chondrosarcoma) to 77.4 Gy (for chordoma) of radiation over the course of 7 to 8.5 weeks, as outlined in Figure 9 (B).

The long term goal of this research is to improve treatment outcomes and quality of life in patients with tumors of any origin, who undergo treatment with radiation. We hope that the results of this translational research may ultimately enable the predication of patients at risk of fracture and allow intervention before fracture occurs.

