5. TREATMENT PLAN

CONFIDENTIAL

This document is confidential. Do not disclose or use except as authorized.

Study participants will receive treatment as determined by their treating physicians at the Massachusetts General Hospital for Malignant Bone Tumors of the Sacrum. This may be radiation alone or pre-operative radiation therapy followed by surgery. The treatment plan including MRI and CT imaging is determined by the clinical situation and not by the study. Patients planned for surgery typically receive pre-operative MRI of their pelvis and/or sacrum. In addition, patients often receive a pelvic or sacral computed tomographic image. A CT of the chest is performed to evaluate for pulmonary metastasis. Figure 9 outlines the current standard radiation treatment options. Study participants may also receive radiation therapy as part of another clinical trial. For surgical candidates, the standard treatment includes pre-operative radiation of 50.4 Gy, followed by a recovery period of approximately 4 to 5 weeks. Surgery involves removing the malignant tumor in the sacrum in one piece, preferably with a cuff of normal tissue around the tumor. After approximately 6 weeks of recovery, to allow the surgical incision to heal, the patient is treated with another 19.8 Gy up to 27 Gy of radiation postoperatively depending on the final margin status (higher for gross residual disease), as outlined in Figure 9(A). If the wound is not healed or there is another medical reason to delay adjuvant radiation, then radiation may begin later. The patients are typically followed every 3 months with an MRI of the pelvis/sacrum to evaluate for a local recurrence. A CT scan is often ordered if there is a concern for a fracture. In addition, patients typically receive a chest x-ray at 3 months and 9 months after surgery. A chest CT is ordered at 6 months and 12 months after surgery. The same protocol is used during the second year of follow up. Non-surgical candidates receive 72 up to 77.4 Gy of radiation depending on the histology (72 Gy for osteosarcoma and chondrosarcoma and 77.4 Gy for chordoma) as outlined in Figure 9 (B).

Figure 9: Radiation Treatment Flowchart

CONFIDENTIAL

This document is confidential. Do not disclose or use except as authorized.

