Bone biopsies will be performed on patients enrolled in the Surgical Arm of the study. Each patient will undergo two biopsies. At the time of each biopsy we plan to collect two bone samples. Figure 10 shows the location of the planned biopsy sites. The first biopsy (the control) will be taken from the iliac wing of the pelvis. This area lies outside of the radiated field, and will serve as a normal bone control. The second biopsy will be taken from the irradiated part of the sacrum. Bone biopsies will be evaluated for the end points of dynamic histomorphometry, and possible radiation-induced woven bone and bone mineralization abnormalities. Micro-CT will be performed on half of the bone samples prior to embedding to evaluate 3D trabecular microstructure. Biopsies that will be used for dynamic histomorphometry will be stored in 10% buffered formalin at room temperature in a dark space. We will send the biopsies to [name] at Columbia University for analysis. Transfers will be done in batches using FedEx. After all studies have been performed we will label the biopsies with a code. The key to the code will connect the biopsy with the subjects health information. The key to the code will be kept in a password protected computer of the principal investigator. Biopsies will be stored either at room

[figure not shown]
CONFIDENTIAL

This document is confidential. Do not disclose or use except as authorized.

temperature (embedded specimen) or frozen (fresh specimen) at the Endocrine Unit Research Laboratory of the Massachusetts General Hospital.

Figure 10 shows the location of two biopsy sites.

Figure 10: Location of the Planned Bone Biopsy Sites.

Biopsies will be done at the time of the scheduled tumor surgery. Sacral tumors are removed in stages. The first stage is done via anterior exposure, allowing access to the iliac crest. We will collect these samples first. Using a 7,5mm Rochester trephine two bone samples will be removed from the superior apex of the iliac wing in the midline (as defined as a point midway between the anterior superior and posterior superior iliac crests). In most cases, the biopsy site will be accessible through the incision made for the anterior approach. However, in those rare cases when the biopsy site is not accessible via the incision made as part of the standard of care, then a separate small incision (at most 3 cm long) will have to be made.

[figure not shown]

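### The rationale asks about radiation over 70 Gy, but the surgical arm's only post-radiation QCT and every sacral biopsy follow a prescribed 50.4 Gy

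*Combined protocol and SAP*

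**What the plan says.** **The dose of interest.** Section 2.1 (Rationale) says "we propose to investigate the impact of high dose radiation (over 70 Gy) on human bone metabolism, architecture, and mechanical properties". The same section ties its concern to that level: "At high doses (70 Gy and above), the rate of bone-related complications increases dramatically". It also states a dose-response: "The detrimental effects of radiation increase proportionally with the dose delivered". Objective 1.2.1 (density by QCT) and objectives 1.3.2 to 1.3.4 (biopsy work) refer to high doses without a figure in Gy; 1.3.2, for example, reads "To analyze the effects of high doses of radiation on the structure and mechanical properties of bone".

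**The surgical arm (20 patients).** Section 2.1 says of these patients "They receive 50.4 Gy of photon/proton beam radiation before surgery", then "After the tumor is surgically removed, patients receive another 19.8 Gy of radiation, for a total dose of 70.2 Gy". Section 5 gives a range for the later part: "the patient is treated with another 19.8 Gy up to 27 Gy of radiation postoperatively depending on the final margin status". It starts after about 6 weeks of recovery.

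**When bone is measured.** Section 8.3.2 puts the first QCT before any radiation in both arms. The surgical arm's second QCT is immediately before surgery, 10 weeks after the first. No later scan is planned because metal artifact from the instrumentation would prevent analysis. Section 8.3.3 says "Biopsies will be done at the time of the scheduled tumor surgery", in the surgical arm only, with an out-of-field iliac control and a sacral sample. Section 5.2 limits the non-surgical arm (10 patients, 72 to 77.4 Gy) to blood samples and QCT.

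**The primary endpoint.** Section 14.1.1 defines it as the change in trabecular density between the start and the close of radiotherapy.

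**The concern.** The dose in the rationale and the dose behind most of the bone measurements differ, and no section says so. Micro-CT, nanoindentation, labeling and histology all use surgical-arm specimens taken before the last part of the radiation course. The density endpoint in the larger arm has the same limit.

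What is at stake is the label on the results. The protocol itself says that effects grow with dose and that complications climb steeply from 70 Gy. An estimate made after 50.4 Gy but reported as the effect of radiation over 70 Gy would describe a different exposure from the one that motivates the study. Section 14.2 says the pilot's numbers are meant to guide later studies, so the wrong dose label would carry forward. The endpoint definition in 14.1.1 also cannot be followed as written in the arm on which the sample size rests.

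**Working it through.** **1. The plan's own figures.** Total surgical dose (2.1): 50.4 + 19.8 = 70.2 Gy, as printed. With the upper post-operative dose in section 5: 50.4 + 27 = 77.4 Gy.

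Power (14.2): change 10 mg/mL, SD of change 15 (printed as mg/dL, taken as mg/mL), alpha 0.05 (taken as two-sided). For a paired t-test, power = P(|T| > t(0.975; n−1)), where T is noncentral t with n−1 degrees of freedom and noncentrality √n × 10/15.

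| n | Noncentrality | Computed power | Stated power |
|---|---|---|---|
| 30 | 3.651 | 0.942 | 0.942 |
| 20 | 2.981 | 0.807 | 0.807 |
| 10 | 2.108 | 0.469 | 0.469 |

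All three reproduce.

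**2. Prescribed cumulative dose at each measurement** (sections 2.1, 5, 8.3.2, 8.3.3 and the calendars in 9.1.1 and 9.1.2).

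| Measurement | Patients | Timing | Prescribed dose by then |
|---|---|---|---|
| Surgical QCT 1 | 20 | Before radiation | 0 Gy |
| Surgical QCT 2 | 20 | Just before surgery | 50.4 Gy |
| Iliac biopsy | 20 | Surgery stage 1 | Control site, out of field |
| Sacral biopsy | 20 | Surgery stage 2 | 50.4 Gy |
| Surgical blood, last three draws | 20 | End of post-operative radiation, then 1 and 4 months later | 70.2 to 77.4 Gy |
| Non-surgical QCT 1 | 10 | Before radiation | 0 Gy |
| Non-surgical QCT 2 | 10 | Six months after first treatment (8.3.2); about 3 months after radiation (9.1.1) | 72 to 77.4 Gy |
| Non-surgical blood, last three draws | 10 | End of radiation, then about 3 and 6 months later | 72 to 77.4 Gy |

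The timing of surgical QCT 2 is internally consistent: about 5.5 weeks of radiation (9.1.2) plus 4 to 5 weeks of recovery (section 5) gives 9.5 to 10.5 weeks, against the 10 weeks in 8.3.2.

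**3. Size of the gap.**
- 70 − 50.4 = 19.6 Gy below the level named in 2.1.
- 50.4/70.2 = 0.718, 50.4/72 = 0.700 and 50.4/77.4 = 0.651 of the full courses.
- On the standard regimen, sacral biopsies after a prescribed 70 Gy or more: 0 of 20. Second QCTs after such a course: 10 of 30, all non-surgical.

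**4. Endpoint timing.** Surgical QCT 2 comes before the post-operative 19.8 to 27 Gy, so it is not at the close of treatment. Non-surgical QCT 2 does follow the full course, but by months, and 8.3.2 and 9.1.1 place it differently.

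**5. Illustration only.** Assume that the 10 mg/mL change belongs to the full dose and scales in proportion to dose. At 50.4 Gy the change would be 10 × 50.4/70.2 = 7.18 or 10 × 50.4/77.4 = 6.51 mg/mL. Power at n=20 would then be 0.529 or 0.454 instead of 0.807. The documents do not say to which dose the 10 mg/mL refers, and the conclusion does not depend on this step.

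**The case against.** The doses and the schedule are stated openly, and the pre-surgery scan has a good reason: instrumentation makes a later one unusable. Biopsy at tumor surgery is likewise the natural opportunity. The study is a pilot, and 14.1.2 calls the biopsy endpoints exploratory. All of this stands. It explains the timing but leaves the description of the results uncorrected.

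A reader might also infer several stronger things that the documents do not support:

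- *That all surgical-arm QCT and biopsies reflect 50.4 Gy.* The first scan is a 0 Gy baseline and the iliac sample is an out-of-field control. The point covers one scan and one biopsy site per patient.
- *That objectives 1.3.2 to 1.3.4 cannot be answered in any patient.* They carry no Gy figure. The 70 Gy level comes from the rationale, which calls 30 to 40 Gy relatively low and does not classify 50.4 Gy.
- *That the dose to the measured bone is known.* These are prescribed doses. No section gives the dose at L1, L2, S1 or the biopsy site, and section 5 allows radiation under another trial, which could change an individual's dose.
- *That the plan pools all 30 patients.* Section 14.2 prints power for 30, but no pooled analysis is specified and 14.3 stratifies by treatment.
- *That a small effect at 50.4 Gy would falsely reassure.* This is speculation: 2.1 describes skeletal complications as common even at 30 to 40 Gy.
- *That nothing is observed after the full course.* The non-surgical QCT and the later serum samples are.

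**Conclusion.** The concern holds in this form. On the standard regimen, the surgical arm's only post-radiation QCT (20 of 30 patients) and every sacral biopsy follow a prescribed 50.4 Gy, which is 72% of 70.2 Gy and 19.6 Gy short of the level named in 2.1. No tissue result observes that level, and the timing in 14.1.1 is not met in the arm that drives the sample size. Density after a full prescribed course is measured only in the 10 non-surgical patients, at a stated power of 0.469.

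This rests on prescribed doses and on patients following the standard schedule. Dose at the measured sites could differ and is not given.

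Severity: should be fixed. It changes what the trial can claim. A stronger rating is not warranted for a pilot with exploratory biopsy endpoints, full-course serum data and a density objective partly served by the non-surgical arm.

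**What to change.** - In 1.2.1, 1.3.2 to 1.3.4 and 14.1.1, state that surgical-arm QCT and sacral biopsy results are effects of the pre-operative course (prescribed 50.4 Gy).
- Reconcile the scan timing in 14.1.1 with 8.3.2 and the study calendars, for each arm.
- State in section 14 that density conclusions about prescribed courses over 70 Gy rest on the non-surgical arm (n=10, stated power 0.469). Do not present any combined n=30 estimate as an over-70-Gy effect.
- Abstract from existing radiotherapy plans the dose delivered to each QCT region and biopsy site by the time of measurement, and report results against it.

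The cost is revised wording, one extra abstracted data item and a less favourable stated power for the over-70-Gy density question. No change to treatment or visits is implied.

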2.2 Study Disease

This study does not focus on a single disease. Instead, the study is concerned with effects of high dose radiation therapy on bone quality in general. For the pilot study, we will focus on patients with primary malignant bone tumors of the sacrum, but the results will most likely be generalizable to other conditions, including metastatic disease.

2.3 Bone Labeling Drugs

2.3.1 *Tetracycline*

Tetracycline is an FDA-approved anti-microbial drug, available in the US in generic form. It has minimal, well-documented adverse effects. Tetracycline can be safely self-administered by the patient in a form of oral pill on outpatient basis. In this study, it will be used as a fluorescent label for dynamic bone histomorphometry studies, in accordance with a well-established protocol. Manufacturer: Varies

2.3.2 *Demeclocycline (Declomycin)*

Demeclocycline is an FDA-approved anti-microbial drug, available in the US in generic form. It is a tetracycline derivative, and has a similar safety profile. All associated adverse effects are minimal and well-documented. Demeclocycline can be safely self-administered by the patient in a form of oral pill on outpatient basis. In this study, it will be used as an accessory fluorescent label (in addition to tetracycline) for dynamic histomorphometry studies, in accordance with a well-established protocol. Manufacturer: Varies

2.4 Correlative Studies Background

[figure not shown]
We hypothesized that bone degradation after irradiation is associated with detectable changes in serum markers, bone metabolism, bone structure and mechanical properties. In order to characterize these changes, we designed a series of *in vivo* and *in vitro* experiments, summarized in

CONFIDENTIAL

This document is confidential. Do not disclose or use except as authorized.

Figure 4.

Figure 4: Experimental Design: Summary of the Proposed Experimental Techniques and Measurements to be Collected in the Study

Data Collection: We will characterize changes in the bone by evaluating the structure and cellular composition of bone, bone metabolism and bone mechanical properties. This figure summarizes the experiments we plan to perform and the data we plan to collect.

2.4.1 *Serum Markers*

A number of circulating serum molecules are used clinically as markers of bone turnover rate and bone remodeling. N-Telopeptide (NTX) is a breakdown products of Type I collagen molecule, which is particularly abundant in bone. It has been shown to be useful in predicting the risk of fractures [32] and other skeletal complications in cancer patients [17]. We will also test serum tartrate-resistant acid phosphatase 5b (TRAP5b). TRAP 5b may reflect different aspects of osteoclast function; osteoclast adhesion, osteoclast number and degradation of non-collagenous proteins [37, 38]. We will use these measurements as markers of *bone resorption*. In addition, we will measure several markers of *bone formation*: osteocalcin (OC) and type 1 procollagen N-terminal (PINP).

In addition to bone-specific markers, we will measure calcium (as part of a standard metabolic panel), phosphate, parathyroid hormone levels (PTH), and 25-hydroxycalciferol as indicators of systemic metabolism that can affect bone health. The changes in serum bone turnover markers are expected to predate fractures, if fractures do occur. While we expect the markers to increase with the onset of radiation, we will follow the trend after the radiation has been discontinued to see if and when the markers begin to return to normal.

[figure not shown]
2.4.2 *QCT*

Quantitative computer tomography analysis (QCT) is a high resolution imaging technique that can detect changes in bone mineralization density and trabecular bone density [20, 33]. Figure 5 (E) shows the difference between two bone types. Cortical bone is thick and solid, and provides the weight-bearing strength of bone. Trabecular bone is porous, and has a woven-like structure. Radiation causes sclerosis of the trabecular bone, rendering it solid and dense, like cortical bone. Despite this increase in density, irradiated bone becomes brittle and prone to fractures. Traditional method of measuring bone density by dual-energy X-ray absorptiometry (DEXA) measures an average density of cortical and trabecular bone. It cannot differentiate between normal bone and fragile, irradiated bone affected by sclerosis. QCT can measure the density of trabecular bone directly. Figure 5(A-C) shows the axial, coronal and sagittal scans of the lumbar vertebral body by QCT. A three-dimensional reconstruction of a slice through the vertebral body allows determination of the architecture of the trabecular bone, as illustrated in Figure 5(D).

Figure 5: Determination of Bone Structure in the Adult Spine by Quantitative CT (QCT)

CONFIDENTIAL

This document is confidential. Do not disclose or use except as authorized.

[figure not shown]
Calculation of the bone mineral density and trabecular bone density by QCT in the adult spine. A. Axial cut through the body of the L1 vertebra showing the difference in density of the cortical bone (bright white) and trabecular bone (gray). B. Coronal and C. Sagittal reconstructions of the same L1 vertebra show the woven porous structure of the trabecular bone. D. A rendered, sagittal slice of 10 mm thickness shows the trabecular structure in 3-D. E. Illustrates the difference in the structure of the cortical and the trabecular bone in the lumbar vertebral body.

Bone density can be calculated from the radiopacity of the bone expressed in Hounsfield units, averaged over a small region of interest (ROIs) as shown in Figure 6. In the lumbosacral spine, ROIs are drawn through the anterior aspect of the L4, the sacral alae, and midline of S1, avoiding any areas of abnormal anatomy or sclerosis due to fractures or degenerative changes. The Hounsfield unit values are then entered into software to calculate values for the trabecular bone mineral density (Tb. BMD) in the region of interest.

Figure 6: Definition of ROI in the Lumbar Spine

CONFIDENTIAL

This document is confidential. Do not disclose or use except as authorized.

Determination of the Regions of Interest (ROI) in the Lumbar Spine. A. Shows the level of the axial cut through which the scan was taken. B. The elliptical area drawn around an area of the lumbar vertebral body is an ROI used to calculate the trabecular bone density.

2.4.3 *Bone Histomorphometry*

[figure not shown]
Histomorphometry is broadly defined as the measurement of the shape or form of a tissue. Bone histomorphometry is a quantitative analysis of bone structure and bone remodeling. It provides valuable information on the amount of bone and its cellular activity. *Static histomorphometry* allows quantitative evaluation of bone structure and cellular content at any particular time point. Undecalcified bone samples embedded in plastic resin are used for this purpose. Cellular content of is evaluated by immunohistochemical staining methods. Changes in bone structure and the volume of mineralized tissue are assessed by micro-computed tomography, quantitative back scatter electron imaging, and nanoindentation.

Dynamic histomorphometry provides a quantitative assessment of the extent of bone formation over a specific period of time (usually 10-14 days). If a fluorescent label, such as tetracycline, is present, it becomes incorporated into the newly formed bone, leaving a clear linear record of the site where mineralization was occurring (see Figure 7). If a second label is given 10-14 days after the first one, one can calculate the *mineral apposition rate* (MAR, mm/day) as the distance between the midpoints of the two consecutive labels, divided by the time interval between the labeling periods. The *bone formation rate* (BFR/BS, mm³/mm²/day) is the amount of newly formed bone seen under the fluorescent microscope divided by the time interval during which the label was given. We will use a quadruple labeling schedule, using two sets of double tetracycline labels which differ in color under fluorescent light. This way we will be able to distinguish the first and second label set. This technique has the great advantage that the patient can serve as his or her own pretreatment control, eliminating problems caused by the large intersite variability in histomorphometric variables [39].

CONFIDENTIAL

This document is confidential. Do not disclose or use except as authorized.

Figure 7: Visualization of Tetracycline Labeled Bone by Fluorescent Microscopy

Tetracycline Double Label. Older bone is bound to the first label and is located further away from the marrow side. Newly mineralized bone is closer to the marrow side, and is bound to the second label, which was administered later in the time course of the experiment.

2.4.4 *Micro-computed tomography (micro-CT)*

Microtomography (micro-CT) is used for in vitro bone studies. It uses a similar technique to conventional X-ray tomography systems (regular CT scans), but with much finer resolution. Morphological parameters of any object can be analyzed with very high precision using three-dimensional reconstructions. The process is non-destructive and requires no special preparation of the specimen. Micro-CT can measure static morphological parameters of bone microscopic architecture. The bone volume fraction (BV/TV), trabecular thickness (Tb. Th.), trabecular separation (Tb. Sp.), trabecular number (Tb. N.), Connectivity density (Conn.D), structure model index (SMI), and trabecular bone pattern factor (TbPf) provide information about the characteristics of the trabecular bone structure. In networks of trabecular bone, connectivity density provides an estimation of the number of trabecular connections per unit volume. The structure model index determines the geometry of the intertrabecular network.

[figure not shown]
2.4.5 *Nanoindentation*

Nanoindentation is a powerful method for investigating the mechanical properties of materials in small dimensions. This is done by pressing a hard diamond tip into the sample of the material of interest with a known amount of force. Traditional indentation methods measured hardness of materials from the area of the “footprint” left in the sample by the diamond tip. Nanoindentation creates “footprints” in the submicrometer range, much too small to examine without a powerful microscope. Instead, it uses specialized depth sensing equipment to make tiny indentations in the surface. At the same time it records the load and displacement of the indenter with very high accuracy and precision. A load-displacement curve is constructed from the recorded values (Figure 8). Experimental data can be interpreted using analytical models to obtain hardness, the elastic modulus, and other mechanical properties.

CONFIDENTIAL

This document is confidential. Do not disclose or use except as authorized.

Figure 8: Schematic Representation of a Typical Load-Displacement Curve

Load-Displacement Curve. A typical Load-Displacement curve is constructed from the load and the displacement of the indenter. It has three distinct portions labeled “load”, “hold” and “unload”. They refer to the corresponding stages of the experiment, during which the load on the indenter behaves differently. When the load is increased, the indenter sinks into the material due to both elastic and plastic deformation (“load”). If the load is held constant, the indenter continues to sink into the material due to time-dependent deformation or creep (“hold”). When the indenter is unloaded, the material recovers by a process that is primarily elastic (“unload”).

We will measure the elastic modulus of bone from the unloading segment of the load-displacement curve using the Oliver-Pharr method. The elastic modulus is a measurement of bone’s ability to resist mechanical stress. Healthy bone is strong and it effectively resists the outside forces exerted on it. When the body is in the upright position, gravity exerts a significant force on the bones of the spine and pelvis causing deformation. Healthy bone resists deformation: it returns to its original form when the force is removed. In contrast, bone weakened by osteoporosis or radiation cannot resist stress exerted by normal activities, like walking. Gravity causes it to deform permanently; even when the force is removed or reduced, the deformation remains. This is the mechanism proposed to explain the development of sacral insufficiency fractures after radiation. We want to measure the elastic modulus of bone in the sacrum before and after radiation to characterize the effect of radiation on the elastic properties. It is exceedingly likely that the pathogenesis of radiation-induced sacral insufficiency fractures is multifactorial. Given this complexity, the ability to isolate the effect of radiation on elastic property makes nanoindentation a uniquely valuable tool for our study.

